9.6.3.2 Other Secondary Objective

The secondary objective of this study is to monitor safety and tolerability in all subjects during the study. All safety analyses will be conducted with the SAF (inferential analyses will not be performed on safety endpoints) and are described in 0.

9.6.4 Exploratory Analyses

The exploratory analyses will be conducted using both the FAS and the PPS. Descriptive statistics as described in 9.1.3 will be provided, unstratified, and also using the stratification factors displayed in section 9.1.1. All data (collected and derived) will be listed.

9.6.4.1 Exploratory Objective 1: NEQ

The exploratory objective 1 is related to the analysis of levels of nicotine over the exposure period in smokers switching from CIG to THS Blade device, Induction Mono device, or Induction Mid device, and in smokers continuing to smoke CIG. It will be done using descriptive statistics (see section 9.1.3) computed on NEQ (see section 5.1.1 for details of NEQ computations)

9.6.4.2 Exploratory Objective 2: Nicotine/Tobacco Product Use

The exploratory objective 2 related to the nicotine/product use will be covered by the statistics computed as described in section 9.5.

9.6.4.3 Exploratory Objective 3: ABOUT – Product Experience

Data from each item of the ABOUT – Product Experience questionnaire will be summarised as categorical (each possible level per item will be displayed). Subscales will be considered as Safety Evaluation.

Confidentiality Statement

Data and information contained in this document are considered to constitute trade secrets and confidential commercial information, and the legal protections provided to such trade secrets and confidential information are hereby claimed under the provisions of applicable law. No part of this document may be publicly disclosed without the written consent of Philip Morris Products S.A

9.6.4.4 Adverse Events

AEs (including SAEs) will be collected from the time of ICF signature until the EOS for each participant (AEs occurring on subjects who are not part of the SAF will only be listed and are not part of the summaries related to SAF).

Any AEs which may occur during the screening period will be captured by the investigational site staff and assessed by the Investigator or designee(s) to establish relationship to study procedures.

During a 3-day Safety follow-up period new AEs/SAEs will be recorded and ongoing AEs/SAEs will be followed-up by the study site.

Information recorded for AEs/SAEs will include verbatim description, start and stop dates and times, seriousness, severity (intensity), causal relationship with IP and study procedures, action taken with IP (e.g., reduced, not changed), other action taken (e.g., treatment administered, if led to the subject's discontinuation from the study), and outcome (e.g., resolved, stabilized).

All safety data will be provided in listings by randomized study arm or a group of enrolled but not randomized subjects, subject, and safety period. The safety periods are defined as:

1. Screening: from Screening visit to baseline
2. Exposure: from Day 1 to Day 5 11:00 PM or early discontinuation date and time
3. Follow-up: from end of exposure to end of Safety follow-up

Unless otherwise specified, summaries will be produced by randomized study arm or a group of enrolled but not randomized subjects and safety periods.

Adverse event data will be used for the primary assessment of safety. Other safety variables monitored in this study will include vital signs (systolic and diastolic blood pressure, pulse rate, respiratory rate), ECG data, spirometry data, clinical chemistry, hematology, urine analysis safety panel, concomitant medications.

The number and percentage of subjects with AEs and SAEs will be tabulated by the Medical Dictionary for Regulatory Activities (MedDRA) system organ class (SOC) and preferred term (PT) for the SAF, overall and by safety period. The number of AEs and SAEs by relatedness to product exposure (including expectedness) and relatedness to study procedures, AEs by severity, and AE by action taken related to the product will be summarized. The number of subjects experiencing an event and the number of events for the SAF will be tabulated. Common adverse events will also be tabulated. Common AEs would be those AEs that have PTs with incidence $\geq 5\%$ in any of the randomized study arms or group of enrolled but not randomized subjects.

Confidentiality Statement

Data and information contained in this document are considered to constitute trade secrets and confidential commercial information, and the legal protections provided to such trade secrets and confidential information are hereby claimed under the provisions of applicable law. No part of this document may be publicly disclosed without the written consent of Philip Morris Products S.A.

Unless specified otherwise, results will be sorted alphabetically by SOC, and by decreasing frequency of the PTs within a SOC. In the event of PTs having equal frequencies, the PTs will be sorted alphabetically within the SOC.

9.6.4.4.1 Serious Adverse Events (Including Deaths)

The number and percentages of SAEs will be summarized overall and by SOC and PT for each randomized study arm or a group of enrolled but not randomized subjects when applicable, for the SAF. Tabulations will include both the number of subjects experiencing an event and the number of events.

Unless specified otherwise, results will be sorted alphabetically by SOC, and by decreasing frequency of the PTs within a SOC. In the event of PTs having equal frequencies, the PTs will be sorted alphabetically within the SOC.

The number and percentage of deaths will be presented if applicable and AEs leading to death will be listed.

All SAE data will be listed.

9.6.4.4.2 Adverse Events Leading to Discontinuation

Subjects discontinuing the study due to an AE will undergo the early termination procedures and will enter the 3-day Safety Follow-Up Period. If there are any AEs leading to discontinuation of a product or the study, they will be summarized overall and by SOC and PT for the SAF.

All AEs leading to discontinuation will be listed.

9.6.4.5 Device Events

All events relating to the device type will be listed, including event description, device type the event relates to, severity of event, AE relationship, proposed solution and onset/stop dates/times. Device events will be classified according to C54451/Medical_Device_Problem_Codes_FDA_CDRH

A summary table of device events will be presented by randomization arm for both the run-in period and randomized exposure period, including:

- Number of device events and the number and percentage of subjects reporting at least one device event.

Confidentiality Statement

Data and information contained in this document are considered to constitute trade secrets and confidential commercial information, and the legal protections provided to such trade secrets and confidential information are hereby claimed under the provisions of applicable law. No part of this document may be publicly disclosed without the written consent of Philip Morris Products S.A

- Number of device events and the number and percentage of subjects categorized by severity of device event (minor, major).
- Number of device events and the number and percentage of subjects categorized by AE relationship (related, not related).
- Number of device events and the number and percentage of subjects categorized by event description.

All device events will be listed; data collected during pre-observational period will not be summarized.

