## Explanation of Terms

The following special terms are used in this protocol:

|                       |   |
|-----------------------|---|
| Alternate subjects    | Subjects who have signed the ICF, have met the inclusion and exclusion criteria, and have been enrolled (completing Screening visit and Admission Day -2), but did not proceed to Baseline Day -1 and have not been randomized due to a sufficient number of subjects available for randomization at that time.

An alternate subject may join the following group if her/his 28-day Screening period has not exceeded. The alternate subject will have to repeat the Admission Day -2 visit to re-confirmed eligibility. |
| Blade device          | Tobacco Heating System (THS) device with Blade technology for Blade stick use   |
| Blade stick           | Tobacco stick designed specifically to be used with the Blade device.   |
| Cigarette(s) (CIG)    | The term 'CIG' refers to commercially available regular cigarettes (manufactured) and excludes hand-rolled cigarettes, cigars, pipes, bidis, and other nicotine-containing products.  |
| Early termination     | Premature termination of exposure to the Investigational Product after the start of the Exposure period in the confinement setting.   |
| End of study (EOS)    | The EOS for an exposed subject is defined as the completion of the 3-day Safety follow-up period either after Discharge on Day 6, or after the date of an Early termination, or after discontinuation of the exposed subject. The EOS of the entire study is the end of the Safety Follow-up Period for the last subject.   |
| Induction Mono device | Tobacco Heating System (THS) device with Induction technology (combined Charger-Holder device for Induction stick use).   |
| Induction Mid device  | Tobacco Heating System (THS) device with Induction technology (device with Induction stick Holder for Induction stick use and separate Charger).  |
| Induction stick       | Tobacco stick designed specifically to be used with the Induction Mono device or Induction Mid device.  |

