## 6.5 Investigational Product Accountability and Adherence

### 6.5.1 Dispensing Investigational Products

CIG for consumption during the confinement period, i.e., on Day -1, and in the CIG arm until end of Exposure period on Day 5 11:00 PM, will be dispensed by the investigational site staff as per the study design.

THS Blade device, Induction Mono device, or Induction Mid device, and corresponding sticks (Blade Regular, Induction Regular) will be dispensed by the investigational site staff for use at the product test on Admission Day -2, and from Day 1 onwards until the end of Exposure period on Day 5 11:00 PM in the corresponding THS arms.

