**Table 7 Time Schedule – Admission Day -2**

| Time               | Procedures  | Additional Information   |
|--------------------|---|--|
| Start of Procedure | Admission Visit Day -2                                    |  |
| Start of the visit | Check-in at site  | CIG use allowed on site on Day -2  |
| Prior enrolment    | Collection of spot urine                                  | 
 
- Drug test
 
- Cotinine test
 
- Pregnancy test (WOCBP)
 
 |
|                    | Body weight   | BMI calculation  |
|                    | Vital signs   |  |
|                    | Smoking history   | TNP Use History questionnaire  |
|                    | Inclusion/exclusion criteria                              |  |
|                    | Information on smoking risks; advice on smoking cessation | Including THS briefing   |
| Prior to breakfast | Enrollment  | After confirmation of the eligibility of the subject   |
|                    | Start of run-in period                                    |  |
| During the visit   | Breakfast   |  |
|                    | Lunch   |  |
|                    | THS product test  | Subject can test THS with three sticks per THS   |
|                    | Concomitant medication                                    |  |
|                    | Concomitant disease status                                |  |
|                    | AE/SAE recording  |  |
|                    | THS product events and complaints                         |  |
| End of the visit   | Subjects remain confined                                  | 11:00 PM stop of smoking   |

Abbreviations:

AE = Adverse event; BMI = Body mass index; CIG = Conventional cigarette(s); FTND = Fagerström test on nicotine dependence; SAE = Serious adverse event; THS = tobacco heating system; TNP = tobacco and/or nicotine containing product(s); WOCBP = women of child-bearing potential.

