| Enrolment   |           | •                      |          |                 |   |   |           |                                |                  |        |
| Tobacco/nicotine product use history e | •         | •                      |          |                 |   |   |           |                                |                  |        |
| FTND  |           |                        | •        |                 |   |   |           |                                |                  |        |
| Randomization                                     |           |                        | •        |                 |   |   |           |                                |                  |        |
| Informing subjects about allocated                |           |                        |          | •               |   |   |           |                                |                  |        |
| Collection of cigarette butts                     |           |                        | •        | •               | • | • | •         | •                              |                  |        |
| Collection of used THS sticks                     |           |                        |          | •               | • | • | •         | •                              |                  |        |
| B: BoExp in blood: COHb                           |           |                        | •        | •               | • | • | •         | •                              |                  |        |
| U: 24-h urine for BoExp (see below)               |           |                        | •        | •               | • | • | •         | •                              |                  |        |
| ABOUT-Product Experience                          |           |                        | •        | •               | • | • | •         | •                              |                  |        |
| AE/SAE recording f                     | •         | •                      | •        | •               | • | • | •         | •                              | •                |        |
| THS product events and complaints                 |           | •                      |          | •               | • | • | •         | •                              | •                |        |

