8.4 Safety Set (SAF)

The safety population will consist of all the subjects enrolled in the study with at least one exposure to THS (product test at Admission Day -2), and who have at least 1 valid value for a safety assessment. The SAF will be analyzed according to actual exposure arm.

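### SAP 9.6.4.5 tabulates run-in device events by randomization arm, so events from the Day -2 product test cannot be read by the device that was used

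*SAP*

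**What the plan says.** SAP 9.6.4.5 sets the layout: "A summary table of device events will be presented by randomization arm for both the run-in period and randomized exposure period". The summary items are the overall count, severity, relationship to an AE, and event description. Device type is an item of the listing only. The section closes with the statement that "data collected during pre-observational period will not be summarized".

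The only other mention of run-in is in Protocol Table 7, where "Start of run-in period" stands on Day -2 after the enrolment row and before the product-test row. The SAP's own safety periods (9.6.4.4) are screening, exposure and follow-up.

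Protocol 6.5.1 dispenses THS "for use at the product test on Admission Day -2, and from Day 1 onwards until the end of Exposure period". The schedules of events (Protocol Appendix A, SAP 13.1) mark the row "THS product events and complaints" on Day -2 and from Day 1, but not on Day -1.

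On the analysis set, SAP 9.6.3.2 says "All safety analyses will be conducted with the SAF", and SAP 8.4 defines that set as "all the subjects enrolled in the study with at least one exposure to THS (product test at Admission Day -2", provided they have a valid safety value. Randomization is not required. Alternate subjects (Protocol, Explanation of Terms) "have been enrolled (completing Screening visit and Admission Day -2), but did not proceed to Baseline Day -1 and have not been randomized".

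**The concern.** The incidence of device malfunctions and product complaints is a stated secondary endpoint (Protocol 3.3, SAP 3.3). A reader of the run-in rows would want to know how often each device failed at first use. An arm assigned afterwards cannot answer that. The CIG and Mid columns could show events on devices those subjects were not assigned, and the Blade and Mono columns would each mix two devices.

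The closing sentence of the section may instead remove the same events from the summary. A programmer working from the SAP cannot tell which table to build.

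Subjects who used THS at the test but were never randomized also have no named place in this table.

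**Working it through.** The documents give no figure for this layout, so there is none to reproduce. The check sets the passages side by side and then counts.

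**1. THS use before Day 1.** The screening demonstration involves no use (Protocol 7.4.1). On Day -1 subjects smoke their own cigarettes (Protocol 4.1, SAP 4.1). That leaves the Day -2 test, described as Blade and Induction Mono with up to three sticks each (Protocol 4.1, 6.2.1, 7.4.1; SAP 4.1). Protocol 6.5.1 names all three devices in its dispensing sentence, but every description of the test itself names two. Randomization follows on Day -1 (SAP 4.6.1).

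**2. Order of enrolment and test.** Test before enrolment: Protocol synopsis and 4.1, SAP 4.1. Test after enrolment: Protocol 7.4.1, Table 7 and Appendix A footnote a; SAP 13.1 footnote a.

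**3. Possible readings.**
- Test after enrolment and inside the run-in, with pre-observational meaning something earlier: test events are shown under the later arm.
- Pre-observational covers Day -2: test events are not summarised, and the run-in rows have no source.
- Test before enrolment, with run-in starting after enrolment as in Table 7: the run-in rows are empty.

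**4. Size on the first reading.** Inputs: 80 randomized 1:1:1:1 (SAP 6), so 80/4 = 20 per arm; two devices per subject; at most three sticks per device. Assumption: all 80 test both devices. Mono and Mid take the same Induction Regular sticks (Protocol 6.1.1), so stick events are counted separately.

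| Later arm | Subjects | Device tests | Match on device | Sticks (max) | Match on stick type |
|---|---|---|---|---|---|
| Blade | 20 | 40 | 20 | 120 | 60 |
| Mono | 20 | 40 | 20 | 120 | 60 |
| Mid | 20 | 40 | 0 | 120 | 60 |
| CIG | 20 | 40 | 0 | 120 | 0 |
| Total | 80 | 160 | 40 | 480 | 180 |

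- Device: 160 - 40 = 120 tests do not match (120/160 = 75%).
- Sticks: 480 - 180 = 300 at most do not match (300/480 = 62.5%).
- The layout also splits one common test into four groups. One affected subject reads as 1/20 = 5.0% in an arm column, against 1/80 = 1.25% by device.

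**5. Non-randomized subjects.** The SAP names a group for them in 9.3 (Safety Set demographics), 9.6.4.4 (default layout), 9.6.4.4.1, 9.6.4.6.1 and 9.6.4.6.2. Section 9.6.4.5 does not. Their number is not given, so the size of this gap cannot be stated.

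**The case against.** The strongest defence is that nothing is lost. Run-in and exposure rows are separate, every device event is listed with its device type, and no inference is made on safety endpoints. Showing pre-randomization data by later arm under a period label is a common layout and does not by itself blame the arm's product. This stands and is why the point is minor. It does not help a reader who wants the test's incidence by device.

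The table shells are a separate document and might add device rows or further columns. That is possible, but the SAP states the grouping, and unseen shells cannot be assumed to override it.

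The default in SAP 9.6.4.4 includes enrolled subjects who were never randomized. It applies unless something else is specified, and 9.6.4.5 does specify randomization arm. It may still be meant to apply, so one cannot say that these subjects are excluded; they have no named column. They have no exposure-period data in any case.

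Four stronger readings are tempting and are not supported:
- **That test events will certainly appear under CIG and Mid.** This holds on only one of the three readings.
- **That 75% of events will be misplaced.** The 75% counts tests; the documents give no event rates.
- **That everything in the Mid column is foreign to that arm.** For stick events, Mid subjects testing Mono used their own arm's stick type.
- **That the layout is an undeclared departure from the protocol.** Protocol 12.7 does make actual exposure arm its default for safety summaries, but its device sentences set no columns of their own. The SAP is aligned to protocol version 3.0, whereas the protocol supplied is version 2.0. The SAP describes that amendment as a change in blood-sampling time, so 12.7 may be unchanged, but this cannot be checked.

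**Conclusion.** The point holds as a minor reporting fault. As written, SAP 9.6.4.5 cannot give product-test device incidence by device, and its undefined terms leave open whether those events are summarised at all. Where they are shown by arm, the label fails to identify the device in 120 of 160 subject-device tests, assuming all 80 randomized subjects test both devices. The stick figure of 300 of 480 is a maximum, reached only if every subject uses three sticks per device. How many events this would affect, and how many non-randomized subjects it concerns, cannot be derived from the documents. Exposure-period counts, listings, the primary and key secondary analyses, alpha and power are untouched.

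**What to change.** In SAP 9.6.4.5:
1. Tabulate Day -2 product-test device events by device used (Blade, Induction Mono). The denominator is all Safety Set subjects who used that device, including those never randomized.
2. Limit the by-arm device table to the randomized exposure period.
3. Define run-in and pre-observational period, or delete both terms.
4. Reconcile the passages that place the product test before enrolment with those that place it after. The order decides whether subjects who test and then decline count as enrolled, and so whether they belong to the denominator in item 1.

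The cost is one small descriptive table and a few lines of SAP text. Device type and onset and stop times are already among the listed items, so no new data are needed for enrolled subjects. If the test is placed before enrolment, those who decline are screen failures, for whom Protocol 11.1.3 keeps only limited data; they would then lie outside the Safety Set and the table.

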9.6.4.6 Medications, Physical Findings, Vital Signs and Other Observations Related to Safety

Clinical Laboratory Evaluation

[Table 12](#) details the clinical laboratory parameters.

Table 12. Clinical Laboratory Parameters Safety Panel

Hematology	Clinical Chemistry	Urine Analysis
- Hematocrit	- Albumin	- pH
- Hemoglobin	- Total protein	- Bilirubin
- Mean corpuscular hemoglobin	- Alkaline phosphatase	- Glucose
- Mean corpuscular hemoglobin concentration	- Alanine aminotransferase	- Nitrite
- Mean corpuscular volume	- Aspartate aminotransferase	- Red blood cell traces
- Platelet count	- Blood urea nitrogen	- Protein
- Red blood cell count	- Creatinine	- Specific gravity
- White blood cell (WBC) count	- Gamma-glutamyl transferase	
- Differential WBC count:	- Fasting glucose*	
• Neutrophils	- Lactate dehydrogenase	
• Basophils	- Potassium	
• Eosinophils	- Sodium	
• Lymphocytes	- Total bilirubin	
• Monocytes	- Direct bilirubin	
	- Total cholesterol	
	- Triglycerides	

Descriptive statistics for actual values and changes from baseline will be produced for the clinical chemistry, hematology, and urinalysis safety panel, for the SAF.

Confidentiality Statement

Data and information contained in this document are considered to constitute trade secrets and confidential commercial information, and the legal protections provided to such trade secrets and confidential information are hereby claimed under the provisions of applicable law. No part of this document may be publicly disclosed without the written consent of Philip Morris Products S.A.

All laboratory data will be listed for all subjects.

